### f) Procedures Involved in the Human Research

All eligible subjects will undergo visits at screening, baseline (week 0), visit 8 hours after week 0, week 1, week 2, visit 8 hours after week 2, week 3, and week 4 (end of study). The parameters of study drug dosing are as follows: isradipine as utilized in this trial will be administered twice daily. Isradipine will be titrated as follows: baseline (week 0) 5 mg/day BID; Week 2 increase to 10 mg/day BID if 5 mg was well-tolerated. Dosing will be flexible based on side effects with a maximum=10 mg/day. If 5 mg cannot be tolerated, the subject will be discontinued. Dosing was based on package labeling for hypertension and prior studies in Parkinson's disease (Simuni et al. 2010).

	Protocol Title:	A Molecular Approach to Treat Cognition in Schizophrenia: Ca 2+ Channel Blockade
	Principal Investigator Name/Contact Info:	[name] [contact]
	Primary Contact Name/Contact Info:	[name] [REDACTED]
	Date Revised:	May 16, 2017
	Study Number:	HSM# 12-0031, GCO# 12-0679, GCO# 13-1987

Measures described in detail below:

Safety Outcome Measures

- The Side Effects Checklist (SEC; physician administered) and side effect self-report form – (all visits)
- Vital signs including blood pressure (standing/supine – all visits)
- Blood pressure check within 8 hours of first dose. Staff contact number will be given to subject in case there are any problems before the 8 hour BP check (week 0). An additional blood pressure check 8 hours after increased dosage (week 2).
- Electrocardiogram (ECG); chemistry panel and CBC via blood draw (approximately 2 TSP blood drawn); urinalysis (screening & week 4)
- Urine toxicology (screening)
- Urine pregnancy test for women of childbearing potential (baseline)
- Abnormal Involuntary Movement Scale (AIMS) and Simpson Angus Scale (SAS) (all visits)
- Beck Scale for Suicidal Ideation (SSI) and Columbia Suicide Severity Rating Scale (C-SSRS) (all visits)

Clinical/Symptom Measures

- Structured Clinical Interview for the DSM-IV (SCID-IV) (screening)
- Symptom rating scales including the Brief Psychiatric Rating Scale (BPRS), the Scale for the Assessment of Negative Symptoms (SANS), the Hamilton Rating Scale for Depression (HRSD), the Clinical Global Impression Scale (CGI), the Clinician Administered Rating Scale for Mania (CARS-M) (all visits)

Neurocognitive/Functional Measures

- MATRICS Consensus Cognitive Battery\* (baseline & week 4)

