Data from this study may be used in medical publications or presentations. The information will be de-identified so that individual subjects cannot be recognized and the information will no longer be considered PHI. The information that is collected for research will be analyzed for many years and it is not possible to know how long this analysis and follow-up will take. Therefore, participants are allowing access to this information indefinitely.

Subjects will only be identified with a numerical code in compliance with HIPAA regulations. Raw subject data will be secured in double locked physical control. Digitized raw data will be similarly de-identified using coding and will be secured on an MS SQL server with Windows integrated security.

	Protocol Title:	A Molecular Approach to Treat Cognition in Schizophrenia: Ca 2+ Channel Blockade
	Principal Investigator Name/Contact Info:	[name] [contact]
	Primary Contact Name/Contact Info	[name] [REDACTED]
	Date Revised:	May 16, 2017
	Study Number:	HSM# 12-0031, GCO# 12-0679, GCO# 13-1987

Data analysis plan is included below. All analyses will be based on an intent-to-treat sample of subjects who received at least one dose of isradipine. Since the missing values may be dependent on the observed outcomes, we assume the missing data mechanism to be missing at random, and hence a mixed models analysis will be used to assess the treatment effect of isradipine with fixed effects for week and first order autoregressive covariance structure to evaluate change over time for all of the primary outcome measures. Cognitive measures will be handled differently, as these will only be collected at two time points – if missing data are substantial (or a complete visit is missing), subjects' data will not/cannot be meaningfully analyzed.

*Primary Analyses* will test the following hypotheses based on our specific aims:

To determine the feasibility of 4 weeks of isradipine on cognitive outcomes in SZ.  
Hypothesis: We will successfully recruit up to 80 stable schizophrenia and schizoaffective patients

To determine the safety of 4 weeks of isradipine on cognitive outcomes in SZ.  
Hypothesis: The frequency of new or worsened side effects (clinician-rated; self-reported; lab-based) will not be significantly different from baseline to end of study visit.

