A Fisher exact test will compare time-points by frequencies of new or worsened (compared with baseline) side effect severity ratings – this will be done for all side effects assessed by the SEC.

Differences on laboratory measures (chemistry panel, etc.) will be tested using repeated measures ANCOVA (baseline and week 4) and changes in vital signs (specifically blood pressure) will be assessed using mixed model ANCOVA, to incorporate data at each weekly visit.

Differences on SAS and AIMS total scores will be examined by calculating the  $\tau$ -b rank correlation between score and week for each subject and comparing the distribution of these trend scores with the Conover-Salsburg rank test.

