### **j) Withdrawal of Subjects**

If they choose to consent to the study and are eligible to begin the trial, they will be closely monitored and will visit with the study coordinator and study physician. Side effects will be rated weekly at each visit using an adverse events checklist completed by a study physician. Subjects with an exacerbation of psychosis/depression/mania on a 2-point CGI-change score will be discontinued and treated appropriately by the study physician. Suicidal ideation will be assessed at each visit with the Beck (SSI) and the Columbia Suicide Severity Rating Scale (C-SSRS). Significant suicidal ideation will be addressed immediately using the standard clinical response at ISMMS (evaluation at the walk-in clinic/psychiatric emergency room for potential need to hospitalize). Subjects at risk for suicidal behavior will be discontinued. Subjects with any other clinical worsening as noted by study physician, and any instance of an SAE will be discontinued. In addition, subjects who exhibit any inability to follow the protocol will be discontinued and withdrawn from the study.

To ensure orderly termination from the study, the study physician would meet with the subject to discuss termination and discontinuation of medication. Safety measures would be collected and a follow-up visit by phone would be scheduled to further ensure safe discontinuation. Discontinuing isradipine does not require a taper. We will schedule an in-person visit if necessary after the follow-up visit by phone to address any remaining concerns the subject may have.

Subjects may withdraw from the study for any reason at any time by contacting the principal investigator or any of the research staff. It is also possible to withdraw permission for the use and disclosure of any protected information for research, but it must be done in writing to the principal investigator. In the event permission is withdrawn, information that was already collected may still be used if that information is necessary to complete the research study.

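### The primary safety hypothesis covers self-reported side effects, but the plan specifies no analysis of the self-report form

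*Combined protocol and SAP*

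**What the plan says.** The plan treats side effects in three places.

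- **Hypothesis (section 5h, Primary Analyses).** The safety hypothesis reads: "The frequency of new or worsened side effects (clinician-rated; self-reported; lab-based) will not be significantly different from baseline to end of study visit". The parenthesis names three sources.
- **Data collection (section 5f, Safety Outcome Measures).** The first item is "The Side Effects Checklist (SEC; physician administered) and side effect self-report form", scheduled for all visits. These are two instruments, one administered by the physician and one completed by the subject.
- **Analysis (section 5h, after the hypotheses).** "A Fisher exact test will compare time-points by frequencies of new or worsened (compared with baseline) side effect severity ratings". The sentence then sets its scope: "this will be done for all side effects assessed by the SEC". Laboratory measures get a repeated measures ANCOVA at baseline and week 4. For vital signs, "changes in vital signs (specifically blood pressure) will be assessed using mixed model ANCOVA". SAS and AIMS totals get a per-subject trend score and a rank test.

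Section 5j also describes weekly side-effect rating, and there too the rater is the physician: "Side effects will be rated weekly at each visit using an adverse events checklist completed by a study physician". The self-report form is named only in section 5f. Self-reported side effects are otherwise mentioned only in the wording of the hypothesis.

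**The concern.** A hypothesis that lists its sources promises that each will be examined. Here the analysis sentence fixes a narrower scope than the hypothesis. An analyst who follows it would test the checklist, the laboratory values, blood pressure and the movement scales, and would then report on a hypothesis that also names self-report. A finding of no significant difference would be read as covering what subjects said about themselves when that source had not been analysed.

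The source matters for this drug. The common side effects that section 6 lists for isradipine include headache, dizziness, palpitations, fatigue and constipation. These are known mainly from what the subject says. Laboratory tests, blood pressure readings and movement scales would largely miss them. Under the plan as written, they reach the analysis only if the physician records them on the checklist.

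There is also a prespecification problem. The form is collected but has no assigned use, so whether and how to use it could be decided after the data are seen.

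**Working it through.** No arithmetic applies. The documents state no event rate, alpha, power or margin for the safety tests, and there is no figure in the plan to reproduce. The check matches each source named in the hypothesis to an instrument and then to an analysis.

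| Source named in the hypothesis (5h) | Instrument collected (5f) | Analysis specified (5h) |
|---|---|---|
| Clinician-rated | SEC, all visits; also SAS and AIMS, all visits | Fisher exact test on SEC items; trend scores and rank test for SAS and AIMS |
| Lab-based | Chemistry panel, CBC and urinalysis at screening and week 4 | Repeated measures ANCOVA |
| Self-reported | Self-report form, all visits | None |

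Blood pressure is a further safety measure with its own mixed model. It is not one of the three named sources.

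Counts: 3 sources named, 2 with a specified analysis, 3 − 2 = 1 without. Of the 2 side-effect instruments listed together in section 5f, 1 is analysed.

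Two other passages could in principle fill the empty cell:

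1. *The general mixed-model sentence in section 5h.* It applies to the primary outcome measures as a group and models change over weeks. It names neither the self-report form nor side-effect frequencies. Side-effect frequencies are given their own test a few paragraphs later, and that test is limited to the SEC. The general sentence therefore does not clearly reach the form.
2. *The safety review in section 5i.* The investigator summarises safety outcomes after each 5 completers. The form is listed among the safety measures, so it may well be looked at there. That is a monitoring step and not a test of the hypothesis, and the form is not mentioned.

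Neither passage supplies an analysis, so the cell stays empty.

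**The case against.** The strongest reply is that this is a gap in wording and not in the trial. The data are collected at every visit, so nothing is lost if the form is analysed later. The first clause of the analysis sentence speaks of severity ratings without naming an instrument, and the reference to the SEC could be read as defining the list of effects and not the only rater. The physician may also see the form before completing the checklist. These points have some weight. But section 5h itself separates clinician-rated from self-reported effects, section 5f lists two instruments, and no passage says that self-report feeds into the SEC. If the wider reading was meant, one sentence would settle it.

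A second reply concerns the remedy: an incidence with an interval is not the baseline-to-end comparison that the hypothesis describes. That is true of a raw incidence. An effect counted as new or worsened against the subject's own baseline has that comparison built in. It also avoids repeating on a second form a Fisher comparison in which no subject can be new or worsened at the baseline visit itself.

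A reader might go further and make three inferences that the documents do not support:

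- *That the SEC is the source most exposed to open-label bias, so the conclusion will understate the burden.* Subjects also know that they take isradipine, and section 6 says they will be taught about hypotension and its symptoms. Expectation can act on both instruments, and nothing in the plan ranks them.
- *That self-report plays no part in safety at all.* The review in section 5i may use it. What is missing is a specified analysis.
- *That the shortfall can be put in percentage points.* This would need an incidence and a capture rate, neither of which is given. It would also have to treat the checklist as a subset of self-report, although a physician may elicit effects that a subject does not write down.

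**Conclusion.** The concern holds as a coverage gap. One of the three sources named in a primary safety hypothesis is collected at all visits and has no specified analysis, because the plan limits the side-effect frequency test to the SEC. Followed as written, the safety conclusion would claim more than was examined.

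The size is that one source in three. The effect on the reported incidence is unknown, and so is the degree to which the two instruments would disagree. The conclusion rests on taking the scope clause at its plain meaning and on the absence of any statement that self-report is carried into the checklist. It does not rest on any view about which instrument is the more accurate.

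The plan should be corrected, because the gap touches a primary hypothesis and the data to close it are already being collected. It does not invalidate the trial, and the other specified safety analyses are unaffected by it.

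**What to change.** In the safety analysis text of section 5h, add the self-report form to the side-effect analysis:

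- Out of all subjects who received at least one dose, report the number with any new or worsened effect against baseline by SEC and, separately, by self-report, each with an exact 95% interval.
- Add the number by either source as a supporting summary. It should not decide the hypothesis: without a control arm, combining two checklists also gathers background complaints that cannot be attributed to the drug.
- State that the safety hypothesis is read on both sources and not on the SEC alone, so that a disagreement between them is reported as such.
- State how many dosed subjects have no self-report form after baseline, since they would otherwise pass silently as having no event.

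Deleting self-report from the hypothesis would also make the two passages agree, but it would leave data collected at every visit unused.

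The cost is a few sentences in the plan and some extra tabulation. No visit or instrument is added. The reported side-effect incidence may be higher than one based on the SEC alone.

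### The primary safety hypothesis rests on an uncounted set of separate tests, with no stated alpha, deciding measure or multiplicity rule

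*Combined protocol and SAP*

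**What the plan says.** The safety hypothesis is in section 5h (Data Management and Confidentiality), under Primary Analyses: "The frequency of new or worsened side effects (clinician-rated; self-reported; lab-based) will not be significantly different from baseline to end of study visit". It spans three sources of side effects and is worded as one statement.

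The tests follow directly after it:

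- **SEC:** "A Fisher exact test will compare time-points by frequencies of new or worsened (compared with baseline) side effect severity ratings", and "this will be done for all side effects assessed by the SEC".
- **Laboratory:** "Differences on laboratory measures (chemistry panel, etc.) will be tested using repeated measures ANCOVA (baseline and week 4"). Section 5f collects "chemistry panel and CBC via blood draw" and a urinalysis, without listing analytes.
- **Blood pressure:** "changes in vital signs (specifically blood pressure) will be assessed using mixed model ANCOVA", using every weekly visit. Section 5f records it standing and supine.
- **Movement scales:** "Differences on SAS and AIMS total scores will be examined by calculating the" rank correlation with week in each subject, followed by a rank test on those trend scores.

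No test is named for the self-reported side effects that the hypothesis includes. The protocol gives no alpha, number of SEC items, number of analytes, deciding measure, combining rule or error-rate control. Up to 80 patients are planned, open label, with no comparator described.

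**The concern.** A hypothesis that predicts no significant difference, examined through many separate tests, needs a rule that turns the results into one verdict. Section 5h gives none. On the literal reading, any significant item counts against the hypothesis, and with enough tests some items will be significant even if isradipine changes nothing. On a looser reading, the investigators decide which significant items matter once they have seen them. Either way, the answer to a primary aim is not fixed in advance.

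This would remain if every single test were valid and correctly sized. It is separate from whether Fisher's test suits two visits by the same patients, and from whether non-significance shows safety.

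**Working it through.** The protocol states no figure to reproduce. Everything below is conditional on assumptions, marked as such.

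**Inputs from the protocol.** N up to 80 (section 5c). A Fisher test per SEC item, laboratory tests, blood pressure, SAS and AIMS (section 5h). Eight common side effects are named in section 6; they are examples, not the SEC list.

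**Assumptions.** Two-sided alpha 0.05; no true change; test counts as shown.

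**1. Independent tests at a true 5%.** P(at least one p<0.05) = 1 − 0.95^k.

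| k | Chance of a false signal |
|---|---|
| 3 (blood pressure, SAS, AIMS, one test each) | 14.3% |
| 11 (those plus the eight named effects) | 43.1% |
| 13 | 48.7% |
| 14 | 51.2% |
| 20 | 64.2% |
| 40 | 87.1% |

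The 50% line is crossed at k = 14.

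**2. Correlated tests.** With equal pairwise correlation between normal test statistics (numerical integration), the number needed to pass 50% is 18 at correlation 0.3, 30 at 0.5 and 101 at 0.7. For 40 tests the risk is 74.5%, 57.1% and 37.5%.

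**3. SEC items with the planned Fisher test.** SEC items were simulated from a latent-normal model (between-item correlation 0.2, same-item correlation across visits 0.6, prevalence 10–20% at both visits, N = 80). Fisher's test compared prevalence at the two visits. P(any item p<0.05) was about 13–14% for 20 items and 25–27% for 40; repeated runs move these by a few points. At N = 40, 20 items gave 8–12%. The rates are low because an exact test on few events runs below 5%, and because ignoring the pairing of positively correlated visits makes it more conservative still. For 20 items the implied size per item is about 1 − (1 − 0.135)^(1/20) = 0.7%. An exact McNemar test, which uses the pairing, gave 36–43% for 20 items in the same model, but it is not the planned test.

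**4. Sets combined, treated as independent of each other.** SEC is taken as 20 items at 13.5%.

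- With 20 laboratory and blood-pressure tests at correlation 0.3 (53% on their own): 1 − 0.865 × 0.47 = 59%.
- The same at correlation 0.5 (42% on their own): 1 − 0.865 × 0.58 = 50%.
- With only blood pressure, SAS and AIMS: 1 − 0.865 × 0.857 = 26%.

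**5. A different reading of the SEC comparison.** If new-or-worsened status makes the baseline count zero by definition, Fisher's test inflates instead: 6/80 against 0/80 gives p = 0.028, and a 5% background rate gives a false signal on 21% of occasions per item. That is a separate defect, which multiplicity adjustment would not cure.

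**The case against.** The strongest reply is that the protocol never says one p<0.05 defeats the hypothesis. That rule is an inference, and so is counting blood-pressure means and SAS/AIMS trend scores towards a sentence about side-effect frequency. This is correct. The supportable criticism is that the plan has no combining rule, not that it has adopted a bad one.

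A reader might go further and infer that dozens of 5% tests, one for every analyte, mean a harmless drug would usually show a significant safety change. The documents do not support that. They give neither the 5% nor the counts, and refer only to laboratory measures in general. Fisher-tested SEC items contribute modestly under the two-visit prevalence reading, and strong correlation or few laboratory tests keeps the total below one half.

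A reader might also infer that the verdict could not tell a harmful drug from a harmless one. That is not shown: a harmful drug would produce more and larger signals.

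It is also fair that chance findings err on the cautious side, and that patient safety is managed through weekly review and review after every five completers (section 5i) and the discontinuation rules (sections 5j and 6), not through these p-values. That limits the harm to patients. It does not settle how the primary safety aim is to be answered.

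**Conclusion.** The concern holds as a gap in the decision rule: a primary hypothesis is examined by an uncounted set of tests, with nothing stating how they yield a verdict. Its size is conditional. At an assumed 5%, the tests countable from the text give 14%; adding 20 SEC items gives about 26%; adding 20 laboratory and blood-pressure tests to 20 SEC items gives about 50–60%. Calling a false signal more likely than not therefore requires, for example, 14 or more roughly independent tests at a true 5% size, which is plausible only if laboratory results are tested analyte by analyte.

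The direction matters. The hypothesis predicts no significant difference, so a Bonferroni correction alone would make the drug easier to call safe. Non-significance is weak evidence here in any case: in simulation at N = 80, even a paired exact test on one SEC item had about 12% power for a rise from 15% to 20%.

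**What to change.** In section 5h, replace the verdict of no significant difference with estimation:

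- Report the change in each SEC item, laboratory analyte, blood-pressure measure, SAS and AIMS as an estimate with a 95% interval, labelled descriptive signal detection. State how many items and analytes there are, and how self-reported effects will be summarised.
- Where p-values are shown, state the alpha and give Benjamini-Hochberg adjusted values beside the raw ones within each family.
- State that one item-level p<0.05 neither confirms nor refutes the safety hypothesis, and that non-significance is not evidence of safety.
- Optionally add a per-patient overall description, such as the proportion of dosed patients with any new or worsened side effect. With 80 patients the 95% half-width is at most about 1.96 × √(0.5 × 0.5 / 80) = 11 percentage points.

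A net SEC score (items worse minus items better) should not be the sole verdict. Improvements would cancel harms, harm confined to a few items would be diluted, and the self-reported and laboratory parts of the hypothesis would drop out.

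The cost is analysis-plan wording; no new data or patients are needed. The safety aim would no longer end in a yes/no test, and adjusted p-values are less sensitive, which is why raw estimates and p-values stay in the report.

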	Protocol Title:	A Molecular Approach to Treat Cognition in Schizophrenia: Ca 2+ Channel Blockade
	Principal Investigator Name/Contact Info:	[name] [contact]
	Primary Contact Name/Contact Info:	[name] [REDACTED]
	Date Revised:	May 16, 2017
	Study Number:	HSM# 12-0031, GCO# 12-0679, GCO# 13-1987

disease; **9.** Any drug known to interact with isradipine. **10.** History of GI strictures; **11.** Abnormal lab or ECG at screen. **12.** Significant suicidal ideation at baseline (HRSD item 3 > 2). Concomitant Medications: Practical and ethical considerations prevent an exclusive focus on medication-free patients; however, we will limit participation to individuals taking at least one and no more than 2 concomitant antipsychotic medications and we will exclude subjects who have received ECT within 12 months. Medication load will be incorporated as covariates in statistical analyses using chlorpromazine (CPZ) equivalents.

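### The lab part of the primary safety hypothesis is about how often new or worsened effects occur, but the only named lab analysis compares lab values, so it does not answer that hypothesis

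*Combined protocol and SAP*

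**What the plan says.** Section 5h, under the primary analyses, states the safety hypothesis: "The frequency of new or worsened side effects (clinician-rated; self-reported; lab-based) will not be significantly different from baseline to end of study visit". The outcome is a frequency, and lab-based effects are one of its three sources.

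The same section then assigns the tests. A Fisher exact test compares frequencies of new or worsened severity ratings, and its scope is set by the words "this will be done for all side effects assessed by the SEC". For labs the plan says: "Differences on laboratory measures (chemistry panel, etc.) will be tested using repeated measures ANCOVA (baseline and week 4". Blood pressure has a mixed model, and the SAS and AIMS scores have a rank-based trend test. No ECG analysis is named.

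Section 5f gives the sampling times: "Electrocardiogram (ECG); chemistry panel and CBC via blood draw (approximately 2 TSP blood drawn); urinalysis (screening & week 4". It treats screening and week 0 as separate visits ("All eligible subjects will undergo visits at screening, baseline (week 0), visit 8 hours after week 0") and uses the baseline label for another test in the same list: "Urine pregnancy test for women of childbearing potential (baseline".

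Exclusion 11 in Section 5b reads "Abnormal lab or ECG at screen", without a threshold.

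**The concern.** The hypothesis asks how many patients develop a new or worsened lab abnormality. The named analysis asks whether the average lab value changed. A handful of patients with large changes can leave the average almost where it was, and changes in opposite directions cancel.

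The framing makes this matter. The hypothesis is supported when no significant difference is found, so a test that is weak against uncommon abnormalities tends to return the favourable answer. The trial could report no significant lab change, and take the lab part of the safety hypothesis as met, while several patients had marked abnormalities at week 4.

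Two smaller gaps lie beside this. The lab model refers to a baseline value, while the schedule labels its two lab times screening and week 4 and never says that the first serves as baseline. The ECGs are collected, and Section 6 lists arrhythmias among the rare reported effects, yet no analysis names them.

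**Working it through.** **Hypothesis against analysis.** The documents state no alpha, power, variance or event rate for the safety analyses, so there is no figure to reproduce. The first check is a comparison of Section 5h with itself.

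| Source of side effects | Quantity in the hypothesis | Named analysis | Yields a frequency? |
|---|---|---|---|
| SEC items | frequency of new or worsened | Fisher exact test | yes |
| Lab measures | frequency of new or worsened | repeated measures ANCOVA | no |

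No section defines a lab abnormality, a threshold for worsening, or a frequency summary for labs.

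**How much a test of averages can miss.** All inputs below are assumptions except n, which is the stated maximum in Section 5c.

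- n = 80 complete pairs of screening and week 4 values.
- Each value has SD 1, with correlation r of 0.7, 0.8 or 0.9 between the two times.
- k patients shift by +3 SD and the others have no true change.
- The test is a two-sided paired test at 0.05. With two time points and no covariates, the repeated measures analysis reduces to this. Section 5b would add medication load as a covariate, which is ignored here.

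For k = 4 and r = 0.7:

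- Mean change = 3 × 4/80 = 0.15 SD.
- SD of change without shifts = √(2(1 − r)) = √0.6 = 0.77.
- The shifted patients also widen the spread: √(0.6 + 9 × 0.05 × 0.95) = 1.01.
- Typical test statistic = 0.15 / (1.01/√80) ≈ 1.3, against a critical value of about 2.0.

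Simulated rejection rates (20,000 or 40,000 runs per cell):

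| Patients shifted by +3 SD | r = 0.7 | r = 0.8 | r = 0.9 |
|---|---|---|---|
| 2 of 80 | 8% | 8% | 9% |
| 4 of 80 | 20% | 23% | 30% |
| 8 of 80 | 66% | 78% | 93% |

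If the 4 shifts go two up and two down, the rejection rate is 1% or less. The weakness therefore concerns uncommon or mixed-direction abnormalities. With 8 patients shifted the same way, the test of averages does reasonably well.

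**What a count would report.** Exact (Clopper-Pearson) 95% intervals on assumed counts:

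- 4/80 = 5.0%, interval 1.4% to 12.3%.
- 0/80 = 0%, upper limit 4.5%.

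**Why the count needs criteria.** Suppose a 95% reference range and no drug effect. The chance that a value in range at screening is out of range at week 4 is 3.5%, 3.0% and 2.1% for r = 0.7, 0.8 and 0.9. Over 20 independent analytes (assumed), the chance of at least one such value is 1 − (1 − p)^20, which is 51%, 45% and 35%. Bare reference limits would therefore produce many chance findings.

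**The case against.** The strongest reply is that the data are adequate and the safety oversight is real. Much of this stands, and it limits the point in five ways.

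- **Baseline.** A reader might infer from the schedule that no baseline lab sample exists. The documents do not support that. Chemistry, CBC and urinalysis are taken at screening, before any dose, and with only two lab times the baseline in the model can hardly mean anything else. The gap is an undefined label.
- **Answerability.** A reader might also infer that the lab question cannot be answered at all. It can be, because the screening and week 4 results contain what a count needs. What fails is the named analysis.
- **Exclusion 11.** It is tempting to say that everyone enrolled was normal at screening, so any week 4 abnormality is new. The criterion has no threshold. Under 95% reference limits on 20 independent analytes, a literal reading would exclude 1 − 0.95^20 = 64% of people with ordinary values. If it is applied by clinical judgement, patients with minor deviations can enrol. Each week 4 result therefore has to be compared with that patient's own screening value.
- **ECG.** An ECG is not plainly lab-based, so its omission does not cause the lab mismatch. It is a separate gap, and the open-ended wording in the lab sentence leaves some doubt whether ECGs were meant to be included.
- **Monitoring.** Section 5i requires patient-by-patient review, recording of all adverse events, and a summary of safety outcomes after every five completers. A marked abnormality would probably be noticed. But this is monitoring without stated lab or ECG criteria. It reduces the consequence and does not supply the missing analysis.

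**Conclusion.** The concern holds as a mismatch between hypothesis and analysis. The lab part of the primary safety hypothesis concerns a frequency, the frequency test is confined to SEC items, and the one named lab analysis compares values. Followed as written, the plan would judge the lab part with a test that does not address it.

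That conclusion rests on the text of Section 5h alone. The size rests on assumed inputs: under them the test of averages would miss 4 markedly shifted patients of 80 in roughly 70% to 80% of trials, and 2 of 80 in more than 90%. Other shifts, correlations or numbers of complete pairs would change these figures, and Section 5c promises only up to 80 patients. The sponsor should make the change, which is cheap and uses planned measurements. The baseline label and the ECG summary are clarifications to make at the same time.

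**What to change.** In Section 5h:

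1. Make the analysis for the lab part of the hypothesis a per-patient count and proportion, with exact 95% confidence interval, of new or worsened clinically significant lab abnormalities at week 4. Judge each against that patient's own screening value, by criteria that the study physicians fix before the data are analysed.
2. Keep the repeated measures ANCOVA as a secondary analysis of average change.
3. State that the lab baseline is the pre-dose screening sample, because Section 5f draws labs only at screening and week 4.
4. Summarise the screening and week 4 ECGs in the same way, as a separate item.
5. Include early-termination labs or ECGs only where they are already collected. Section 5j says safety measures are taken at termination but does not say which, so the plan should state whether these are among them.

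The cost is some plan wording, agreement on the criteria, and the extra tables. No new sample or visit is needed. The small downside is that individual abnormalities become visible, so the safety statement may look less favourable.
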